4. ANALYSIS SETS (POPULATIONS FOR ANALYSIS)

Population	Description
Enrolled	All participants who signed the informed consent document.
Evaluable	All participants who signed the informed consent document, met all inclusion/exclusion criteria, and had at least one immunogenicity assay value available for analysis.

5. GENERAL METHODOLOGY AND CONVENTIONS

5.1. Hypotheses and Decision Rules

Not Applicable as this is a descriptive study.

5.2. General Methods

5.2.1. Analyses for Binary Endpoints

For carriage results, the exact 2-sided 95% confidence intervals (CIs) (Clopper-Pearson CIs) will be provided for the proportions of subjects with VT or serotype-specific carriage.

The exact CIs (Clopper-Pearson) for the various proportions of individual groups will be computed using the F distribution. If r is the number of responses and n is the number of subjects, then it follows that $p=r/n$ is the estimate of the proportion of responses. An exact 95% CI can be computed by solving the following 2 equations. For the lower limit P_L ,

$$p_L = \frac{rF_L}{(rF_L + (n - r + 1))}$$

and for the upper limit P_U ,

$$p_U = \frac{(r+1)F_U}{(n-r)+(r+1)F_U}$$

where F_L is the quantile from the F distribution for $\alpha=0.025$, with numerator degrees of freedom equal to $2r$ and denominator degrees of freedom equal to $2(n-r+1)$. F_U is the quantile from the F distribution for $\alpha=0.975$, with numerator degrees of freedom equal to $2(r+1)$ and denominator degrees of freedom equal to $2(n-r)$. When r equals 0, F_L should be set equal to 1.0 so P_L equals 0. When r equals n , F_U should be set equal to 1.0 so P_U equals 1.0.

The CI using the F distribution is described in Collett (1991)¹ and implemented in SAS PROC FREQ.

5.2.2. Analyses for Continuous Endpoints

For each of the 13 serotypes contained in 13vPnC Cohort and also Non-13vPnC Cohort, GMCs of IgG and GMT of MOPA will be calculated along with 2-sided 95% CIs, which will be constructed by back transformation of the CIs for the mean of the logarithmically transformed IgG/MOPA computed using Student's t distribution. In addition, the 2-sided 95% CI on the geometric mean ratios (GMRs) (the GMC of 13vPnC Cohort to the GMC of Non-13vPnC Cohort and the GMT of 13vPnC Cohort to the GMT of Non-13vPnC Cohort) for all 13 serotypes will be also provided and those 95% CIs will be constructed by back transformation of the CIs for the mean difference of the measures on the logarithmically transformed scale(IgG/MOPA) using Student's t distribution.

A multiple regression model will be used with the log concentration or log titers as a dependent variable. Independent variables will include cohort (13vPnC or unvaccinated), 13vPnC VT carriage status, and the interaction of the cohort and carriage status, as well as the confounding variables (age at enrollment, sex, season of enrollment). Adjusted GMCs (or GMTs) and adjusted geometric mean ratios (GMRs) along with 95% CI will be estimated based on this model. The (GMRs) will compare antibody levels between:

1. Within 13vPnC Cohort: VT-carrier + vs VT-carrier -
2. Within Non-13vPnC Cohort: VT-carrier + vs VT-carrier -
3. 13vPnC Cohort vs Non-13vPnC Cohort
4. Within VT-carrier +: 13vPnC Cohort vs Non-13vPnC Cohort
5. Within VT-carrier -: 13vPnC Cohort vs Non-13vPnC Cohort

Additionally, serotype-specific GMC/GMT (unadjusted) and associated 95% CI will be provided for each 13vPnC VT carriage status (Yes/No), for both 13vPnC cohort and unvaccinated cohort. GMRs (unadjusted) (GMC/GMT of VT- carrier + vs GMC/GMT of VT-carrier -) within 13vPnC Cohort and within unvaccinated Cohort, and GMRs (unadjusted) (GMC/GMT of 13vPnC Cohort vs GMC/GMT of Non-13vPnC Cohort) within

VT-carrier + group and within VT-carrier group and associated 95% CIs will be calculated using Student's t distribution for the mean difference of the measures on the logarithmically transformed scale (IgG/MOPA).

If model adjusted GMCs, GMTs, GMRs are not estimatable (e.g., due to limited data), then only unadjusted GMCs, GMTs, GMRs and associated 95% CIs will be presented.

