5.3.1. Immunogenicity Data

Immunogenicity data collected for this study are the results of immunologic assays performed by the National Institutes for Food and Drug Control (NIFDC) on the blood samples collected.

The Lower Limit of Quantitation (LLOQ) in micrograms per mL ($\mu\text{g/mL}$) for each serotype is shown in Table 2.

Table 2. The LLOQ in Micrograms per mL from NIFDC

Serotype	LLOQ
1	0.02
3	0.03
4	0.02
5	0.03
6A	0.03
6B	0.03
7F	0.04
9V	0.02
14	0.04
18C	0.02
19A	0.02
19F	0.03
23F	0.03

Antibody concentrations above LLOQ are considered accurate and their quantitated values will be reported. The Limit of detection (LOD) was established as 50% of the LLOQ. Values below the LLOQ or denoted Below Limit of Quantification (BLQ) will be set to **0.5 \times LOD** for analysis.

The NIFDC's OPA LLOQ in titers for all serotypes was set as 8. For the results of antibody titers that are below the LLOQ, or denoted as BLQ, $0.5 \times \text{LLOQ}$ will be assigned for analysis.

No other missing assay data will be imputed in the analyses. All immunogenicity analyses will be performed after the imputation of the antibody concentrations or antibody titers that are below the LLOQ.

For each serotype's antibody concentrations or antibody titers, the number of subjects with missing values at each blood sampling point will be provided.

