6.1. Primary Endpoint(s)

6.1.1. Primary Analysis

For each cohort, children will be assigned to 2 groups: Participant in whom a 13vPnC vaccine type (VT) strain has been isolated from the respiratory tract, and participant from whom a 13vPnC VT strain has not been isolated from the respiratory tract (VT carrier versus without VT carrier). Therefore, a total of 4 subgroups are available: 13vPnC cohort with VT carrier; 13vPnC cohort without VT carrier; unvaccinated cohort with VT carrier; unvaccinated cohort without VT carrier.

For each of the 13 serotypes contained in 13vPnC, the IgG concentration and MOPA titers will be transformed in logarithm scale. Crude (unadjusted) geometric mean concentrations (GMCs) and geometric mean titers (GMTs) and 95% confidence interval (CI) will be calculated for the 4 cohort/carriage subgroups.

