6.1.2. Sensitivity/Supplementary Analyses

Not applicable.

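### Setting every MOPA titer below 8 to 4 and then applying a Student t interval gives a zero-width GMT interval in an all-floor cell, and too narrow a one in small, mostly floor cells

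*SAP*

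**What the plan says.** On titers at the floor, SAP 5.3.1 states: "The NIFDC's OPA LLOQ in titers for all serotypes was set as 8". It continues, "For the results of antibody titers that are below the LLOQ, or denoted as BLQ", half the LLOQ is assigned, which is 4 for all 13 serotypes. The order of steps is explicit: "All immunogenicity analyses will be performed after the imputation of the antibody concentrations or antibody titers that are below the LLOQ".

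On intervals, SAP 5.2.2 says that cohort-level GMT intervals are "constructed by back transformation of the CIs for the mean of the logarithmically transformed IgG/MOPA computed using Student's t distribution". SAP 6.1.1 adds that crude GMTs with 95% CIs "will be calculated for the 4 cohort/carriage subgroups", for each serotype, and names no other interval method. The unadjusted GMR intervals in SAP 5.2.2 also use Student's t on the log scale.

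Three places might have held a safeguard, and none does:

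- The fallback in SAP 5.2.2 applies when adjusted estimates cannot be obtained, and "then only unadjusted GMCs, GMTs, GMRs and associated 95% CIs will be presented". It leads back to the same t intervals.
- SAP 6.1.2, on sensitivity analyses, reads "Not applicable".
- SAP 5.3.1 promises the number of missing values for each serotype, but not the number below the LLOQ.

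**The concern.** A t interval takes its width from the spread of the observed log titers. Substituting one constant removes the spread among all titers below 8. In a cell with only floor values, the data say that every titer is below 8 and that the share at or above 8 is probably small. The printed interval says that the GMT is known exactly.

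With one or two quantifiable titers in a small cell, the width rests on those few values, and samples that happen to contain too few of them give an interval that is both too low and too narrow.

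The study has no hypotheses, so no decision turns on this. The interval is, however, the planned statement of uncertainty for the primary endpoint, and nothing else in the planned output would show that a narrow interval reflects the assay floor.

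**Working it through.** **Cell sizes (protocol 3.3; SAP 3.1).** 3,800 per year x 2 years x 5% = 380 eligible vaccinated children, as the protocol states. 380 x 30% = 114, given as about 100. With a 1:2 ratio the total is about 300. The unvaccinated MOPA subset equals the number of vaccinated children tested, so each cohort has at most about 100 MOPA results before the split by carriage. The carriage rate is not given. If 20% of 100 tested children carried a vaccine type, that subgroup would have n=20.

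**All-floor cell (no assumption needed).** The interval is exp(m ± t(0.975, n−1) × s/√n), where m and s are the mean and SD of the log titers. If every titer is set to 4, then m = log 4 and s = 0, so the output is 4.0 (4.0, 4.0) for any n ≥ 2. If a share f of titers lies below 8, the chance of such a cell is f^n:

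- n=20: 0.80^20 = 1%; 0.90^20 = 12%; 0.95^20 = 36%.
- n=8: 0.80^8 = 17%.

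**Mostly-floor cell (simulation, 40,000 replicates per setting).** Assumed, because the documents are silent: quantifiable titers are lognormal with GMT 128 and log SD 1.2, truncated at 8. The target is the mean log titer after the SAP's own substitution, so any bias from the value 4 itself is left out. Coverage of the nominal 95% interval:

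| Share below 8 | n=20 | n=100 |
|---|---|---|
| 30-50% | about 95% | 94-95% |
| 70% | 93% | 94-95% |
| 80% | 91% | 94-95% |
| 90% | 84% | 92-93% |
| 95% | 63% | 90% |

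The misses are one-sided. At n=20 with 90% below 8, and GMT varied over 64-256, the interval lay below the true value in 15-17% of runs and above it in 0.2%. A separate calculation treating all titers as one lognormal distribution (log SD 1.0 to 2.0) gave 80-85% at n=20 with 90% below, in line with the table.

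**Unadjusted GMR intervals.** With equal shares below 8 in both groups (n=20 versus 80), a pooled t interval covered 95-96%. With unequal shares it does not hold: n=20 at 80% below versus n=80 at 95% below gave 82%.

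The reason can be shown approximately. Ignoring truncation, the variance of a substituted log titer is f(1−f)(log 128 − log 4)² + (1−f) × 1.2², where (3.466)² = 12.01.

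- f=0.80: 0.16 × 12.01 + 0.20 × 1.44 = 2.21.
- f=0.95: 0.0475 × 12.01 + 0.05 × 1.44 = 0.64.
- Pooled variance: (19 × 2.21 + 79 × 0.64)/98 = 0.94. SE used: √(0.94 × (1/20 + 1/80)) = 0.24.
- Actual SE: √(2.21/20 + 0.64/80) = 0.34.

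The SE used is about 0.7 of the actual one. If both groups are entirely below 8, the GMR interval is 1.0 (1.0, 1.0), again with zero width.

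**What an all-floor cell does tell the reader.** The Clopper-Pearson upper limit for 0 of n is 1 − 0.025^(1/n): 16.8% for n=20 and 3.6% for n=100.

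**The case against.** The strongest reply is that the size of the problem rests on inputs absent from the documents. They give no share below 8, no titer SD and no carriage rate. Over much of the plausible range the interval is sound: 93-95% coverage at n=20 with 30-70% below 8, and 94-95% at n=100 up to 80%. This stands. A reader might infer that the unvaccinated cells will be almost wholly below 8. Nothing in the protocol or SAP shows that for children hospitalised with pneumonia.

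Second, a printed 4.0 (4.0, 4.0) at half the LLOQ is easily recognised as an all-floor cell. That is partly true, but a reader cannot recognise a nearly all-floor cell, because the number below the LLOQ is not planned for reporting.

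Third, it would go too far to say that the plan prints its narrowest intervals exactly where information is least. Zero of 100 at or above 8 is strong information. The fault is that the interval shows the same zero width for 0 of 5 as for 0 of 100.

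Fourth, the equal-share result might suggest that GMR intervals are safe. The unequal-share result shows otherwise, and the plan compares groups whose shares may differ. The 82% depends on a pooled variance; the SAP says only Student's t, so another variance form would give another figure.

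Fifth, suppressing the interval in cells with few quantifiable titers would do harm. A cut-off of fewer than five at or above 8 would remove the interval in 64% of cells with n=8 and 50% below 8, where coverage is about 94%. That objection is accepted.

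**Conclusion.** The point holds in a conditional form. The zero-width interval in an all-floor MOPA cell follows from the SAP's rules alone, and no provision in either document handles it. Under-coverage in mostly-floor cells is certain in direction but not in size: under the stated lognormal assumption it is negligible up to about 70% below 8 at n=20, clear at 90% (84%) and severe at 95% (63%), and mild at n=100. Unadjusted GMR intervals are affected when group sizes and shares below 8 differ, and have zero width when both groups are all floor.

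The documents do not support a claim that many cells will be affected or that any study conclusion would change. The finding covers the crude MOPA intervals only; the adjusted model and the IgG intervals were not assessed. The consequence is false precision in descriptive tables of the primary endpoint.

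**What to change.** Add to SAP 5.2.2:

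- Beside every MOPA GMT, report the number and proportion of titers at or above 8, with the Clopper-Pearson 95% CI already defined in SAP 5.2.1.
- Where no titer in a cell reaches 8, print '<8' with 0/n and that interval, and no t interval. For 0 of 20 the entry would be 0% (95% CI 0% to 16.8%).
- Where both groups in a GMR are entirely below 8, print no GMR interval.
- Where most titers in a cell, or in a group entering a GMR, are below 8, keep the t interval and footnote it as unreliable. Do not suppress intervals by a count of quantifiable titers.

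The cost is a short SAP addition, one extra table column and a footnote. The GMT remains the endpoint, and its interval is kept in every cell with at least one titer at or above 8.

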4.1. Inclusion Criteria

Subjects must meet all of the following inclusion criteria to be eligible for enrollment in the study:

1. Evidence of a personally signed and dated informed consent document indicating that the parent(s)/legal guardian has been informed of all pertinent aspects of the study.
2. Subjects whose caregiver is willing and able to comply with scheduled visits, laboratory tests, and other study procedures.
3. Residents of Suzhou municipal districts (Gusu, New and high-tech, Wuzhong, Xiangcheng, Industrial Park).
4. A diagnosis of clinical pneumonia per SCH standard of care.
5. 5 months to \leq 60 months of age at the time of consent.
6. Vaccination history (ie, vaccine book or picture of vaccine book) is available for confirmation.
 - a. For the 13vPnC cohort: Participants should have received at least 2 doses of 13vPnC prior to hospitalization. There must be a minimum of 2 weeks between the second 13vPnC dose and enrollment.
 - b. For the unvaccinated cohort: Children did not receive any dose of 13vPnC in the past.

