5. STUDY PROCEDURES

The study will be conducted at SCH in Suzhou, Jiangsu province. SCH is located in the central area of Gusu district and is the only tier III children's hospital serving most of the young children in Suzhou.

Children who are residents from Suzhou municipal districts (Gusu, New and high-tech, Wuzhong, Xiangcheng, Industrial Park) admitted to the SCH with diagnosis of clinical pneumonia per SCH local standard will be evaluated by investigator.

Inclusion and exclusion criteria will be evaluated and those that fulfill all inclusion criteria and none of the exclusion criteria will be offered to participate in the study. Once Informed Consent has been obtained from parents or legal guardians of participants (vaccinated patient and control), study procedures may start.

If a patient is eligible for this study, all study-related procedures will be conducted by study personnel within one day. For every study subject enrolled in the 13vPnC cohort, two study subjects that did not receive 13vPnC will be enrolled on the same day (or \pm 7 days) into the unvaccinated cohort. These control subjects will be matched by age (5 to \leq 12 months, $>$ 12 to \leq 24 months, $>$ 24 months to \leq 60 months). In other words, for every subject enrolled in the 13vPnC cohort, two subjects within the same age group who did not receive 13vPnC will be enrolled if the non-13vPnC subjects hospital admission dates are within 7 days (\pm) of the vaccinated subjects.

Treatment and non-study procedures will be provided by the patient's physician as per local standard of care.

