5.2. Visit 1 (Enrollment)

1. Enroll the subject to this study, if eligible, and assign the participant to a study cohort.
2. Obtain and record the subject demography (including date of birth, sex, residence, and number/age of siblings, if any).
3. Obtain and record the subject's significant medical history (see [Section 6.1](#)).
4. For 13vPnC subjects, record date(s) of 13vPnC vaccination based on the patient's vaccine book.
5. Record antibiotic usage for the current pneumonia episode, to include antibiotic name, dosage, and start/stop date.
6. Collect a blood sample (approximately 5 mL) within 24 hours of enrollment. Blood must be drawn from peripheral veins (eg, arm, foot, or scalp veins). Drawing blood from central veins (eg, jugular or femoral veins), which may increase the risk associated with study participation, is not permitted.

7. Enter deep upper respiratory aspirate specimen information if this standard procedure was performed for this episode of pneumonia. The sample can be from before or after the enrollment. If an aspirate was not collected as a standard practice, this should be collected as a study procedure. The aspirate should be collected within 24 hours of enrollment.
8. Adverse events (AEs) that occur within 12 hours after the blood draw or aspirate collection (if collected as a study procedure) should be recorded in the source documents and in the AE section of the CRF.
9. The investigator or an authorized designee completes the CRF.

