8. DATA ANALYSIS/STATISTICAL METHODS

Detailed methodology for summary and statistical analyses of the data collected in this study will be documented in a Statistical Analysis Plan (SAP) and will be maintained by the sponsor.

The number and proportion of subjects with *S. pneumoniae* isolates detected will be summarized for both cohorts: the 13vPnC cohort and unvaccinated cohort. Additionally, the number and proportion of each serotype, serotype included in 13vPnC (VT), and serotypes not included in 13vPnC (non-VT) will be summarized for both cohorts.

For each cohort, children will be assigned to 2 groups: Participant in whom a 13vPnC vaccine type (VT) strain has been isolated from the respiratory tract, and participant from whom a 13vPnC VT strain has not been isolated from the respiratory tract (VT carrier versus without VT carrier). Therefore, a total of 4 subgroups are available: 13vPnC cohort with VT carrier; 13vPnC cohort without VT carrier; unvaccinated cohort with VT carrier; unvaccinated cohort without VT carrier.

For each of the 13 serotypes contained in 13vPnC, the IgG concentration and MOPA titers will be transformed in logarithm scale. Crude geometric mean concentrations (GMCs) and geometric mean titers (GMTs) and 95% confidence interval (CI) will be calculated for the 4 cohort/carriage subgroups.

A multiple regression model will be used with the log concentration or log titers as a dependent variable. Independent variables will include cohort (13vPnC or unvaccinated), 13vPnC VT carriage status, and the interaction of the cohort and carriage status, as well as the confounding variables (age at enrollment, residence location, season of enrollment). Adjusted GMCs (or GMTs) and adjusted geometric mean ratios (GMRs) along with 95% CI will be estimated based on this model. The (GMRs) will compare antibody levels between any 2 of the 4 subgroups, as well as between the 2 cohorts, and between the carriage status.

Additionally, serotype-specific GMC/GMT (or adjusted GMC/GMT) and 95% CI may be provided for each 13vPnC serotype carriage status (Yes/No), for both 13vPnC cohort and unvaccinated cohort. Similar to any 13vPnC VT carriage status, the descriptive comparisons will be presented as GMR (or adjusted GMR) and 95% CI.

All of the analyses are considered as descriptive and no multiplicity adjustment will be made.

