2. INTRODUCTION

This statistical analysis plan (SAP) provides the detailed methodology for summary and statistical analyses of the data collected in Study B1851196. This document may modify the plans outlined in the protocol; however, any major modifications of the primary endpoint definition or its analysis will also be reflected in a protocol amendment.

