6.2. Baseline and Other Summaries and Analyses

6.2.1. Baseline Summaries

Subjects demographics (collected information including, sex, residence, and number of siblings, if any) and medical history will be descriptively summarized.

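### The SAP's adjusted model omits residence, a confounder the protocol names and the design does not match on, and lists sex instead without giving a reason

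*SAP*

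**What the plan says.** Protocol section 8 specifies a multiple regression of log IgG or log MOPA on cohort, VT carriage and their interaction, "as well as the confounding variables (age at enrollment, residence location, season of enrollment". SAP 5.2.2 gives the same model with a different list: "as well as the confounding variables (age at enrollment, sex, season of enrollment".

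On design, Protocol section 5 states "These control subjects will be matched by age" (three bands). It accepts unvaccinated children when their "hospital admission dates are within 7 days" either side of the vaccinated child's. Neither residence nor sex is a matching factor. Protocol 4.1 limits entry to "Residents of Suzhou municipal districts (Gusu, New and high-tech, Wuzhong, Xiangcheng, Industrial Park".

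Residence is available. Protocol 5.2 instructs the site to "Obtain and record the subject demography (including date of birth, sex, residence, and number/age of siblings, if any", and SAP 6.2.1 tabulates it: "Subjects demographics (collected information including, sex, residence, and number of siblings, if any".

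SAP section 2 says "This document may modify the plans outlined in the protocol", and reserves protocol amendments for major changes to the primary endpoint definition or its analysis. SAP 6.1.1, headed Primary Analysis, describes crude GMCs and GMTs only, and SAP 6.1.2 plans no sensitivity analysis.

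**The concern.** Vaccination is observed here, not randomised, and the adjusted estimates exist to remove differences between groups that also relate to antibody level. The protocol judged residence to be one such difference. If the district mix differs between vaccinated and unvaccinated children, and antibody levels differ by district, the cohort comparisons (items 3 to 5 in SAP 5.2.2) keep that confounding. If the mix differs between VT carriers and non-carriers within a cohort, items 1 and 2 are exposed in the same way.

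The two lists also leave the reader unable to tell a deliberate change from a drafting slip. The SAP explains neither the removal of residence nor the addition of sex.

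**Working it through.** **1. The lists against the design**

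| Variable | Protocol 8 model | Matching (Protocol 5) | SAP 5.2.2 model |
|---|---|---|---|
| Age | yes | yes, three bands | yes |
| Season | yes | yes, through admission date | yes |
| Residence | yes | no; entry restricted to five districts | no |
| Sex | no | no | yes |

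Age and season are each handled twice. Residence is the only protocol-named confounder handled by neither route. Restriction narrows its range but does nothing to equalise the five districts between cohorts. The MOPA controls are a simple random draw from unvaccinated children with adequate serum (SAP 3.1), which does not balance districts either.

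**2. Outputs affected**

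The crude subgroup GMCs and GMTs (SAP 6.1.1) and the unadjusted GMRs (SAP 5.2.2) use no covariates, so they are unchanged. Only the model-based GMCs, GMTs and GMRs depend on the list.

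**3. Possible size of the shift**

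The plan gives no figure for this and no data on district mix or on antibody by district, so both inputs are assumptions. Let d be the difference between the compared groups in the share living in higher-antibody districts, and r the antibody ratio between those districts and the others. If district is unrelated to the covariates already in the model, omitting it multiplies the GMR by exp(d × ln r):

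- d = 0 or r = 1: no shift
- d = 0.05, r = 1.2: exp(0.05 × 0.182) = 1.009, a shift of 0.9%
- d = 1/6, r = 1.5: exp(0.167 × 0.405) = 1.070, a shift of 7.0%
- d = 0.30, r = 1.5: exp(0.30 × 0.405) = 1.129, a shift of 12.9%
- d = 0.30, r = 2.0: exp(0.30 × 0.693) = 1.231, a shift of 23.1%

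The direction depends on which cohort has more children from the higher-antibody districts.

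**4. Cost of adding residence**

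Planned numbers (Protocol 3.3): 3,800 × 5% × 2 years = 380 eligible. Then 380 × 30% = 114, which the plan rounds to about 100. At 1:2 this gives about 300 for IgG. MOPA uses equal numbers, so about 100 + 100 = 200.

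With linear age and four seasons (both assumed), the SAP model has 9 parameters: intercept, cohort, carriage, interaction, age, sex and three for season. Five districts add 4, making 13. At fixed residual variance the standard error of the cohort contrast is multiplied by approximately √[1/(1 − R²)] × √[(n − 9)/(n − 13)], where R² is the squared correlation between cohort and district type.

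- Balanced (R² = 0): IgG √(291/287) = 1.007; MOPA √(191/187) = 1.011.
- 60% against 30%, IgG: overall share 0.40, R² = (1/3)(2/3)(0.30²)/(0.40 × 0.60) = 0.083, factor 1.052.
- 60% against 30%, MOPA: overall share 0.45, R² = 0.25 × 0.30²/(0.45 × 0.55) = 0.091, factor 1.060.

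If only half the planned number were enrolled, the balanced factors become √(141/137) = 1.014 (IgG, n = 150) and √(91/87) = 1.023 (MOPA, n = 100).

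**The case against.** The strongest reply is that this is a permitted change with little consequence. The SAP may depart from the protocol. The study is descriptive, with no hypotheses or decision rules. Crude estimates are reported alongside the adjusted ones, and all children come from five districts of one city, admitted to one hospital. All of that stands, and it limits the priority. It does not supply a reason for the change. Nor does descriptive status help an adjusted estimate that leaves out a confounder the protocol chose to adjust for.

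Three stronger readings are tempting, and the documents do not support them.

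- A reader might infer that the SAP breaks its own amendment rule. That rule covers major changes to the primary endpoint or its analysis. The section headed Primary Analysis is crude and unaffected, so whether the rule applies is a matter of judgement.
- A reader might infer from the version history that an unrecorded change was made. That table logs changes between SAP versions, and its version 1 row reads N/A. If the list dates from version 1, no entry would be expected, so the silence shows nothing about intent.
- A reader might infer that the adjusted GMRs will be materially biased, or their confidence intervals will undercover. Nothing in the documents shows a district imbalance or a district difference in antibody. Coverage, and the size of a shift relative to interval width, also depend on how comparison 3 is averaged over carriage, which the SAP does not state. No such figures are claimed here.

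A further fair point is that adding residence loses precision for nothing if district is imbalanced but unrelated to antibody. That loss is small at the planned numbers.

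**Conclusion.** The discrepancy is real and is between the current texts of both documents. Residence is named by the protocol, collected, unmatched and absent from the SAP model; sex replaces it; no reason is given. The consequence is confined to the adjusted estimates. Its size is unknown and may be zero: the 0.9% to 23% range illustrates assumed inputs and is not an estimate for this study, and the upper end needs both a 30-point imbalance and a 2-fold antibody difference within one city. This is a cheap improvement of low to moderate priority, not a defect that undermines the study's descriptive purpose.

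**What to change.** In SAP 5.2.2, make the covariate list *age at enrollment, sex, residence location, season of enrollment*. Enter residence as the five districts of inclusion criterion 3, as main effects only. Note in the SAP that sex is an addition to the protocol's list. Keep the existing fallback to unadjusted estimates where the model cannot be estimated. If residence is left out on purpose, give the reason in 5.2.2 so that the two documents can be reconciled.

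The cost is one line of text and no new data: residence is already recorded, and eligibility requires the district to be known. The statistical price is 4 degrees of freedom. Standard errors rise by about 1% if districts are balanced, and by 5-6% if they are imbalanced by 30 points but unrelated to antibody. If district does predict antibody, the lower residual variance offsets part of this. The price is higher if enrollment falls short of about 300, which is possible because Protocol 3.3 closes enrollment at the end of 2020 whatever the number reached.
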